Quantifying the Influence of Yogic Breathwork on Cerebrospinal Fluid Circulation

Unique Protocol Identification Number: STUDY00019281

National Clinical Trial (NCT) Identified Number: NCT03858309

Principal Investigator: [name]

Sponsor: Oregon Health & Science University

Grant Title: Quantifying the Influence of Yogic Breathwork on Cerebrospinal Fluid Circulation

Grant Number: K99AT010158

Funded by: NCCIH

November 11 2019

Principal Investigator or Clinical Site Investigator:

Name: [name]
Title: Senior Research Associate

Investigator Contact Information:

Affiliation: Oregon Health & Science University
Address: [name]
[contact]
Email: [contact]

1) Protocol Title

Quantifying the Influence of Yogic Breathwork on Cerebrospinal Fluid Circulation

2) Objectives

The purpose of this protocol is to determine the influence of an 8-week yogic breathwork intervention on cerebrospinal fluid (CSF) dynamics among healthy subjects using a non-invasive magnetic imaging (MRI) technique. We will examine this aim by studying the changes in each subject's pre- and post-intervention CSF dynamics using the non-invasive RT-PCMRI technique during two MRI scans (one before and one after the 8-week intervention). This aim will test the hypothesis that a regular yogic breathwork practice will enable participants to sustain slow and rhythmical breathing patterns and create larger modulations in their CSF dynamics.

3) Background

Yogic breathwork (YB) is an appealing mind-body therapy for healthcare management purposes because it is a low-risk and low-cost practice that can be easily learned and performed without any additional equipment. It is important to understand the mechanisms for the benefits of YB practices. Based on our preliminary results, we believe that another - less explored- potential mechanism for the positive effects of YB can be its direct influence on cerebrospinal fluid (CSF) circulation, which to date has not yet been quantified due to lack of non-invasive methodology.

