CSF circulation. CSF, a clear colorless fluid secreted by the choroid plexuses, moves by bulk flow (*macrocirculation*) around the central nervous system (CNS), and ensures the health of the CNS⁶. Impaired CSF circulation can comprise the normal physiological functions of the CNS, which then may contribute to CNS diseases including neurodegenerative conditions⁷. Furthermore, CSF circulation plays a key role in maintaining glymphatic transportation of CSF (*microcirculation*). Recent research efforts^{8,9} have defined a "*glymphatic function*", a brain-wide clearance mechanism facilitates the clearance of solutes and metabolic wastes from the brain interstitium. Sleep and arousal state are critical regulators of glymphatic function, since CSF tracer influx and interstitial solute clearance are increased during both sleep and anesthesia compared to the wakefulness¹, which is associated with slowed amyloid beta clearance and more rapid amyloid plaque deposition². The impairment of glymphatic function underlies the development of CNS diseases in the aging brain remains unknown, so it is critical to better understand the complete mechanisms supporting CSF circulation in the human CNS by i) developing non-invasive approaches to measure CSF circulation, and ii) potentially identifying therapies that can regulate and enhance CSF circulation. For this aim, we recently developed novel non-invasive imaging approaches to quantify CSF dynamics ¹² and we aim to study YB as a potential therapy for regulating and enhancing CSF circulation.

4) Study Design

This study is the K99 phase of the NIH-NCCIH K99/R00 study K99AT010158.

Protocol. The study protocol consists of 20 healthy young subjects undergoing an 8-week intervention (10 subjects in arm 1 and 10 subjects in the active control arm 2), and outcome measures within a 2-week period of pre-and post-intervention. We will test the hypothesis that the yogic breathwork practice with sophisticated breathing practices, compared to active control will enable participants to sustain slow and rhythmical breathing patterns and create larger modulations in their CSF dynamics.

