Post-acquisition, each data set will be examined for quality and completeness by the trained study team.

CSF flow:

- CSF flow data analysis will be performed using a semiautomated pulsatility-based segmentation procedure. The velocity waveform will be averaged over the highly correlated ROI pixels. The maximum and minimum peak values of the averaged CSF flow velocities will then be used for analysis (see details below *Statistical Analysis*).
- The respiration frequency band and the cardiac frequency band will be defined based on the two main distinct peak amplitudes of the frequency spectrum of the averaged CSF velocity waveforms measured with RT-PCMRI.
- The relative contribution of the respiration versus cardiac component of the CSF velocity waveforms will then be quantified by defining a power ratio between respiratory component and the cardiac component.

Respiration and ECG data:

- The pulse ox and respiration data collected during the RT-PCMRI acquisitions will be filtered using a 4th order Butterworth to extract only the respiration and only cardiac component.

Wearable device:

- Respiration data from wearable device collected during the 8-week intervention will be analyzed for the respiration rate and peak-to-peak respiration intervals. If collected, sleep data measured with wearable device will be analyzed to measure the influence of intervention on participants' long-term

sleep patterns objectively.

Self-report questionnaires:

- Response to self-report questionnaires will be analyzed for the statistical analysis to compare the changes in subject's quality of life, sleep, and existing stress levels.

Statistical Analysis

- The major dependent variables will be i) CSF flow metrics maximum and minimum (values of average CSF velocities; relative ratio of respiration vs. cardiac component of the CSF velocity; ratio of the maximum CSF velocity during breathing practices to the average of peak CSF velocities at baseline during natural breathing, ii) respiration rate and peak-to-peak respiration intervals and iii) self-reported questionnaire results. The effects of the interventions on these variables will be tested in a multivariate analysis of variance with repeated measures to compare pre- and post-intervention. An alpha value of 0.05 will be used for statistical significance.

9) Privacy, Confidentiality and Data Security

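### No primary variable or control of follow-up claims is stated; if the MANOVA is joint, its rejection would not by itself support the CSF hypothesis

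*Combined protocol and SAP*

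**What the plan says.** Section 2 (Objectives) gives the purpose as to "determine the influence of an 8-week yogic breathwork intervention on cerebrospinal fluid (CSF) dynamics among healthy subjects". Section 4 (Study Design) states a between-arm hypothesis: that yogic breathwork "compared to active control will enable participants to sustain slow and rhythmical breathing patterns and create larger modulations in their CSF dynamics". The hypothesis therefore has a breathing part and a CSF part, while the purpose is CSF.

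Section 8, Statistical Analysis, begins: "The major dependent variables will be i) CSF flow metrics maximum and minimum". It goes on to the respiratory-to-cardiac ratio and the practice-to-baseline velocity ratio, and then to "ii) respiration rate and peak-to-peak respiration intervals and iii) self-reported questionnaire results". The test follows: "The effects of the interventions on these variables will be tested in a multivariate analysis of variance with repeated measures", to compare before with after. The last sentence is: "An alpha value of 0.05 will be used for statistical significance".

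Neither this section nor the outcome list in section 4 ranks the variables. No hierarchy, follow-up test or adjustment is described anywhere. The text does not say whether the contrast of interest is time or arm by time, or whether the 0.05 is one- or two-sided.

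**The concern.** The trial asks a CSF question, but the plan does not say which test answers it. The singular model and the reference back to all the listed variables suggest one joint MANOVA. Such a test asks whether anything in the set differs, and self-reported scores alone could make it reject. A CSF conclusion would then rest on follow-up tests whose number and error rate are not fixed in advance.

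There is a related gap in the respiration variables. Section 8 says: "Respiration data from wearable device collected during the 8-week intervention will be analyzed for the respiration rate and peak-to-peak respiration intervals". Data collected only during the intervention have no pre-intervention value, so as written they cannot enter a pre-post model. Table 1 does show physiological measures during MRI at both imaging visits, but the plan does not say which recording is meant.

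**Working it through.** **Inputs from the documents.** Alpha is 0.05 (section 8). There are 10 subjects per arm, possibly 13 (section 5a). The CSF list is read as four metrics: maximum, minimum and two ratios. There are two respiration variables. The number of questionnaire scores is not stated. Section 8 speaks of "quality of life, sleep, and existing stress levels", which gives three scores at one per domain, so p = 4 + 2 + 3 = 9. Section 6 names six instruments, so at one score each p = 4 + 2 + 6 = 12.

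**Assumptions.** The plan gives no effect size, SD, correlation or power, so it has no figure to reproduce. Shifts are in SDs of the change score, with complete data. Three correlation patterns are used: A, all zero; B, 0.5 among all scores; C, 0.5 within CSF and within questionnaires, zero elsewhere.

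**Formula.** With two time points, the arm-by-time test is Hotelling's T² on change scores. It is an F test on (p, N−1−p) df with noncentrality λ = (n per arm / 2) × D², where D² = δ′Σ⁻¹δ. Error df with 20 subjects: 20−1−9 = 10, 20−1−12 = 7, and for CSF alone 20−1−4 = 15. With 26 subjects they are 16, 13 and 21. With 20 subjects the error df reach zero at 19 scores, so the score count matters.

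**1. Joint model, CSF and respiration null, questionnaires shifted, 20 subjects.**
- Pattern A, 9 scores, 0.8 SD: D² = 3 × 0.64 = 1.92; λ = 5 × 1.92 = 9.6; critical F(9,10) = 3.02; rejection 27.9%.
- Highest at 0.8 SD (B, 9 scores): D² = (0.64/0.5) × (3 − 0.5×9/5) = 2.688; λ = 13.44; 38.9%.
- Lowest at 0.8 SD (C, 12 scores): D² = 6×0.64/3.5 = 1.097; λ = 5.49; critical F(12,7) = 3.57; 11.9%.

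| Shift (SD) | 9 scores, A / B / C (%) | 12 scores, A / B / C (%) |
|---|---|---|
| 0.3 | 7.4 / 8.4 / 6.1 | 8.1 / 8.4 / 5.8 |
| 0.5 | 12.5 / 16.1 / 8.4 | 14.9 / 15.8 / 7.4 |
| 0.8 | 27.9 / 38.9 / 15.0 | 34.9 / 37.6 / 11.9 |
| 1.325 | 70.5 / 86.0 / 38.1 | 80.3 / 83.5 / 27.6 |

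The last row uses 1.325 SD because one variable alone has 80% power there with 10 per arm.

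**2. False CSF claim in the same setting (simulated).** Suppose the four null CSF metrics are tested at 0.05 without adjustment, but only after joint rejection. At least one is then falsely declared in 2-4% of trials at 0.5 SD (every pattern below 5%), about 3-9% at 0.8 SD and about 6-16% at 1.325 SD. For one given CSF metric the rate stays below 5% throughout. Without the joint gate, at least one of four is declared in 15-19%.

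**3. One model per domain.** Three independent null tests: 1 − 0.95³ = 14.3%. Within the CSF domain, suppose one metric is truly affected and the four-metric MANOVA is followed by unadjusted tests. Another CSF metric is then falsely declared in about 5%, 7% and 11% of trials at 0.5, 0.8 and 1.325 SD. Holm lowers this to about 2%, 3% and 4%.

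**4. Power, 20 subjects.**
- One affected CSF metric of 1.325 SD, uncorrelated with the rest: λ = 5 × 1.325² = 8.78 whatever p is. Power is 80% alone, 50% with 4 scores, 26% with 9 and 17% with 12.
- All four CSF metrics shifted by 1.325 SD, r = 0.5 among all scores. CSF only: D² = 4×1.7556/2.5 = 2.81, λ = 14.0, power 73%. Nine scores: D² = (1.7556/0.5) × (4 − 0.5×16/5) = 8.43, λ = 42.1, power 91%. Twelve scores: 77%.
- The same shifts, but CSF uncorrelated with the other scores (C): λ stays at 14.0, and joint power falls to 41% with 9 scores and 26% with 12.

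**The case against.** Four points on the other side have weight.

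- A single MANOVA at 0.05 is a form of error control: it holds the global-null error at 5%. This stands. A reader might infer that the plan has no error control at all. The documents do not support that; what is missing is control of follow-up and single-variable claims.
- The joint model is a reading, not a statement. Section 8 is organised by domain, has its own questionnaire paragraph, and takes respiration rate and interval from the wearable, which cannot fit a pre-post model as written. One model per domain is not excluded. A reader might infer that no rejection under this plan could be attributed to CSF. That holds only for the joint model.
- The harm may be small. The control arm also practises slow breathing, so modest between-arm questionnaire differences are plausible, and at 0.5 SD the gated false-CSF rate is below 5%. A reader might infer substantial inflation of false CSF claims. That needs shifts of about 0.8 SD or more, is not seen under every pattern even then, and assumes unadjusted follow-up tests that the plan never describes.
- The study is small, and section 5a partly justifies recruitment by intervention development, instrument choice and participant burden. This tempers the weight of the point but does not remove it, because the plan also states a comparative hypothesis and a significance level.

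The unclosed parenthesis in the CSF list may come from PDF conversion and is not counted against the plan. It does make the count of four metrics an interpretation.

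**Conclusion.** The point holds in a limited form and should be fixed. That no primary variable and no control of follow-up claims are stated is plain from the text, and holds on either reading. That a rejection would not by itself support the CSF hypothesis depends on the joint-model reading, held with medium confidence. The 12-39% in step 1 measures how often the omnibus test would reject with CSF unaffected. It is not a false-positive rate for CSF claims, which is the much smaller figure in step 2. All magnitudes rest on assumed shifts, correlations and score counts. None contradicts a figure in the plan, since the sample size is given without a power basis.

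**What to change.** Make the decisive test CSF-only, on the arm-by-time contrast at two-sided 0.05. Either form would do:

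1. One MANOVA restricted to the CSF metrics, followed by Holm-adjusted single-metric tests.
2. One CSF metric, named by the investigators before unblinded data are seen, compared between arms by ANCOVA adjusting for its pre-intervention value.

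State which form is used and list the CSF metrics explicitly. Analyse respiration as a separate secondary domain, and say which respiration recording enters any pre-post comparison. Whether that can be the recording made at the MRI visits is for the investigators to judge, since breathing in the scanner may differ from home practice. Report each questionnaire score separately with a 95% confidence interval, labelled exploratory, and state the number of scores per instrument.

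**Cost.** Only analysis wording changes, but there are trade-offs. The global test's advantage under some patterns is given up (91% with nine scores against 73% for CSF only). Under form 1, a lone affected CSF metric of 1.325 SD has about 45-53% power with 20 subjects. Form 2 has about 80% for the named metric on a change-score calculation (ANCOVA was not computed), but depends on choosing the right one. If respiration is also tested at its own 5%, the chance of any false claim across the two domains can reach 1 − 0.95² = 9.75% under independence, and the plan should say whether that is accepted.

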We plan to recruit 20 healthy subjects (18-65 years; 10 for each of the two groups) from the Portland community through IRB approved flyers posted around the OHSU campus and the city, and advertised in local media. While we do not expect that any participants will voluntarily drop from the study, unavoidable circumstances may arise and we expect to retain enough participants to collect sufficient data on intervention development, decisions on the appropriateness of our instruments, and burden to participants. In order to assure we have sufficient qualitative and quantitative data for this proposed study and any potential lost-to-follow up, we may recruit 13 people for each arm.

b) Inclusion and Exclusion Criteria

Inclusion criteria: 18-65 years of age, able to provide their consent to be in the study, available and able to participate in study activities, who can lie in supine, able to walk 15 feet, who have no prior/current regular mind-body practice inducing breath awareness or training such as yoga, meditation, Ta-Chi, Qi-Gong; a compatible device for physiological data trackers.

Exclusion criteria: inability to provide informed consent, MRI contraindications, need for muscle relaxants or anti-anxiety drugs in order to tolerate MRI, history of neurological disorders, head trauma with loss of consciousness, craniospinal disorders, spinal injury, sleep disorders, allergic or respiratory disorders, major or uncontrolled psychiatric illness or major depression, lung and heart problems, any condition requiring the use of medication that acts on the brain like stimulants, sedatives current substance abuse issues, pregnancy or nursing.

Optimization Scans:

Inclusion criteria: 18-65 years of age, able to provide their consent to be in the study, available and able to participate in 1-hour MRI scan, who can lie in supine, able to walk 15 feet.

Exclusion criteria: inability to provide informed consent, MRI contraindications, need for muscle relaxants or anti-anxiety drugs in order to tolerate MRI.

c) Vulnerable Populations

This study (K99 or R00 phase) will not include any vulnerable populations. We will not collect any information about subjects' status as prisoners, and will actively exclude pregnant women, children, neonates, and adults lacking capacity to provide informed consent.

d) Setting

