- We will assess each subject's response to the following self-report questionnaires during their imaging visits: quality of life (Short-Form Health Survey; SF-36¹⁷), sleep quality (Pittsburgh Sleep Quality Index; PSQI¹⁸), perceived stress (Perceived Stress Scale; PSS¹⁹), Positive Affect Negative Affect Scale - Expanded (PANAS-X)²⁰, The Patient-Reported Outcomes Measurement Information System (PROMIS)²¹, and Cognitive and Affective Mindfulness Scale-Revised (CAMS-R)²². Additionally, we will assess subject's attitudes, expectancy and blinding towards the study.

Physiological Data Tracking:

- **Respiration:** Each subject will be provided with a wearable device in order for the study team to objectively track subject respiration, thus home practice, throughout the intervention. For this purpose, we will use a commercial off the shelf monitor (Spire³). Study staff will assure that these devices remain free of potential identifiers. We will create a respiration tracker account for each user. Subjects will receive instructions on how to utilize the wearable device during the first imaging session.
- **Sleep:** A sleep tracking methodology may be implemented within the study to investigate the effects of the intervention on long-term sleep patterns – using a Fitbit tracker. Study staff will assure that these devices remain free of potential identifiers, and will create a sleep tracking account for each subject. Subjects will receive instructions on how to utilize the wearable device during the first imaging session.

Randomization. Subjects will be told they will be enrolled in one of the 8-week intervention groups for a set of breathing practices. Group allocation will be performed through a sex and age-based randomization by a study team member who will inform the subjects with which group they will be enrolled in. Neither the subject nor the investigator can choose which group the subject will be in. Subjects will be instructed and reminded not to reveal what group they are in during the study assessment visits. They will be instructed to ask the investigator if they have any questions about this kind of study.

i. 8-week interventions.

Breathing practices:

- The yogic breathwork protocol will incorporate breathing practices that will create slow deep rhythmical and large CSF flow patterns. Active control protocol will include slow breathing practices.

Interventions:

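### Read naturally, section 8 puts about 9 to 12 outcomes into one repeated-measures MANOVA on 20 subjects; confining the main test to the CSF metrics would recover power under most plausible correlation structures

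*Combined protocol and SAP*

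**What the plan says.** Section 8, Statistical Analysis, names the major dependent variables in one sentence with three groups.

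- **CSF.** The text reads "CSF flow metrics maximum and minimum (values of average CSF velocities; relative ratio of respiration vs. cardiac component of the CSF velocity", followed by "ratio of the maximum CSF velocity during breathing practices to the average of peak CSF velocities at baseline during natural breathing". That is four metrics: maximum velocity, minimum velocity, respiratory-to-cardiac ratio, and practice-to-natural-breathing ratio.
- **Respiration.** Two variables: rate and peak-to-peak interval.
- **Questionnaires.** The results of the self-report instruments, with no count of scores.

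The test follows: "The effects of the interventions on these variables will be tested in a multivariate analysis of variance with repeated measures". The level follows that: "An alpha value of 0.05 will be used for statistical significance". No primary outcome, follow-up univariate test or alternative analysis is named.

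Section 6, Self-report questionnaires, says "We will assess each subject's response to the following self-report questionnaires during their imaging visits" and names six instruments: SF-36, PSQI, PSS, PANAS-X, PROMIS and CAMS-R. The questionnaire paragraph of section 8 is narrower and speaks of three domains: quality of life, sleep and stress.

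Section 5a gives the size: "We plan to recruit 20 healthy subjects (18-65 years; 10 for each of the two groups". To cover losses it adds "we may recruit 13 people for each arm". Neither figure has a power calculation. The hypothesis in section 4 compares yogic breathwork with the active control on breathing pattern and CSF modulation, so the effect of interest is arm by time.

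**The concern.** A multivariate test pays for each variable it carries. With few subjects, outcomes that do not respond to the intervention use up error degrees of freedom and raise the bar for those that do. The trial's hypothesis concerns breathing and CSF, yet the wording appears to pool three to six questionnaire scores with the CSF metrics in the only planned test. A real and large CSF effect could then be reported as non-significant because of what else was in the model.

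This is separate from the lack of a named primary outcome. Naming one CSF metric as primary and leaving the remaining variables in the same joint test would leave that test just as crowded.

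**Working it through.** **Inputs from the documents.** N = 20, n = 10 per arm, possibly 13 per arm (section 5a). Alpha = 0.05; four CSF and two respiration variables (section 8). Questionnaires: 6 if each instrument in section 6 gives one score, 3 if the domains in section 8 are meant.

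**No figure to reproduce.** The documents give no power, effect size, SD or correlation. Every effect and correlation below is an assumption.

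**Number of variables.** p = 4 + 2 + 6 = 12, or p = 4 + 2 + 3 = 9.

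**Degrees of freedom.** With two arms and two visits, the arm-by-time test is Hotelling's T-squared on change scores, referred to F(p, N − p − 1).

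- N = 20, p = 12: 20 − 12 − 1 = 7
- N = 20, p = 9: 20 − 9 − 1 = 10
- N = 26, p = 12: 26 − 12 − 1 = 13
- N = 20, CSF only, p = 4: 20 − 4 − 1 = 15
- N = 20, p = 19: 0, so the test cannot be computed with 19 or more variables

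**Power.** Noncentral F with noncentrality (n/2) × D², where D is the Mahalanobis distance between arms in mean change.

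*Case 1: one CSF metric differs by 1.325 SD of change (1.32 in the summary figures), all others null and uncorrelated.* D² = 1.325² = 1.756; noncentrality 5 × 1.756 = 8.78 at n = 10. The size was chosen because it gives 80% power for one outcome alone.

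| Variables in the test | Reference F, N = 20 | Power |
|---|---|---|
| 1 | F(1, 18) | 80% |
| 4 (CSF block) | F(4, 15) | 50% |
| 9 | F(9, 10) | 26% |
| 12 | F(12, 7) | 17% |

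At 13 per arm, one variable has 90% and twelve have 30%. At 8 per arm the figures are 69% and 9%. The D needed for 80% power at n = 10 is 1.32 with one variable, 1.81 with four and 3.23 with twelve.

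*Case 2: all four CSF metrics move by 1.325 SD, the other eight are null.* When k of p variables move by d under a common correlation r, D² = [k d² − r k² d² / (1 + (p − 1) r)] / (1 − r). For example, k = p = 4 and r = 0.5 gives (7.02 − 14.05/2.5)/0.5 = 2.81; k = 4, p = 12, r = 0.5 gives (7.02 − 14.05/6.5)/0.5 = 9.72.

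| Correlation within CSF | Correlation of CSF with the other eight | CSF-only: D², power | 12 variables: D², power |
|---|---|---|---|
| 0 | 0 | 7.02, 99% | 7.02, 61% |
| 0.3 | 0.3 | 3.70, 85% | 7.23, 62% |
| 0.5 | 0 | 2.81, 73% | 2.81, 26% |
| 0.5 | 0.5 | 2.81, 73% | 9.72, 77% |

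In the second and last rows the other eight also share the common correlation among themselves. Unaffected variables that correlate strongly with the CSF metrics act like covariates and raise D², which is why the joint test is slightly ahead in the last row.

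**The case against.** **The wording does not fix one model.** A reader might infer that the plan commits itself to a single 12-variable test with 7 degrees of freedom. It does not say so. The variables come in three numbered groups, and one MANOVA per group fits the text: 15 denominator df for CSF, 17 for respiration and 13 for six questionnaires. Under that reading the CSF part already matches the fix below. This stands as a limit on the claim. Still, one list followed by one test described in the singular points more naturally to a joint model, and if separate models were meant, saying so is the same short edit.

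**Twelve is not a floor.** The three domains in section 8 give 9. The wearable is worn only during the intervention, so if the respiration variables come from it they have no pre/post pair; dropping them from 12 leaves 10, with 9 df and 22% power in case 1. Respiration is also recorded during the MRI at both visits, so a pair is available. The range of about 9 to 12 is the safe statement.

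**Low power is not general.** A reader might infer that the joint test has almost no power even for very large effects. The documents give no effect size or correlation to support that. If the four CSF and two respiration variables all move by 1.325 SD, which fits the hypothesis, the 12-variable test has 80%, 72% and 83% power at common correlations of 0, 0.3 and 0.5.

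**Subscales.** A reader might infer that the test fails outright because the questionnaires have subscales. The documents neither count subscales nor say that they are analysed. Only the conditional statement about 19 or more variables at N = 20 holds.

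**The comparison with 80% is uneven.** It sets one pre-named outcome at full alpha against an omnibus test. Testing all twelve separately at 0.05 would carry a 1 − 0.95^12 = 46% chance of at least one false positive if they were independent; under Bonferroni the case 1 effect would have 41% power. This is right, and it is why the fix names one main test rather than only splitting the variables up.

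**Conclusion.** The concern holds in conditional form. On the natural reading, about 9 to 12 variables share one test on 20 subjects, with 10 to 7 denominator df. In case 1 this takes power from 50% in a CSF-only test to 26% or 17%. In case 2 the 12-variable test spans about 26% to 77% against 73% to 99% for CSF only. The CSF-only test wins in most of the structures examined, by as much as 47 percentage points (73% against 26%), and loses slightly in one (73% against 77%).

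The assumptions that carry this are a joint model, the 1.325 SD effect, the correlation patterns, and 10 analysed per arm. Analysing all 26 possible recruits eases the problem without removing it. This is a worthwhile, inexpensive improvement to a stated analysis, not proof that the planned test must fail.

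**What to change.** In section 8, Statistical Analysis, replace the sentence on the multivariate test with text to this effect:

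*The main test is the arm-by-time effect on the CSF block (at most the four listed metrics, F(4, 15) at N = 20), at alpha 0.05. Respiration variables and questionnaire scores, one pre-named score per instrument, are analysed separately for the arm-by-time effect and labelled secondary.*

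Alternatively, name one CSF metric as the main test; this gives the highest power in case 1. Choose between the two before any outcome data are examined. If a joint model of all variables is still wanted, list its variables and keep their number well below 19.

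The cost is a sentence or two, with no new subjects or data. The downside is several secondary p-values without joint error control in place of one omnibus p-value, and some loss of power if the unaffected outcomes turn out to be strongly correlated with the CSF metrics.
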